Gallbladder (GB) disease is extremely common, affecting 10% to 20% of White adults in the United States with the prevalence rising as high as 70% in specific ethnic groups. [1] Up to 5% of patients with gallstone disease become symptomatic within 1-year. [2] The incidence is greatest among obese people placing patients from racial and ethnic minority groups and those from low-income backgrounds at the greatest risk of disease. [3] Elective cholecystectomy is recommended for patients with symptomatic cholelithiasis or biliary colic. [4] Laparoscopic cholecystectomy is a safe and effective treatment that can be performed in the outpatient setting with complication rates ranging from 0.5-6.0%. [5]

Delayed treatment for symptomatic cholelithiasis and biliary colic often results in acute cholecystitis and related diseases that necessitate emergency surgery. [6] For example, patients waiting 20 weeks or more for elective cholecystectomy were more likely to undergo admission for emergency cholecystectomy than those waiting shorter times. [7] Emergent cholecystectomy results in worse outcomes with almost two-fold higher rates of conversion from laparoscopic to open, increased hospital length of stay by an average of over 5 days, increased rates of morbidity (8.8 vs 3.7%) and mortality (2.6 vs 0.5%), and higher costs (mean charge difference over \$6,000) when compared to elective cholecystectomy. [8-10]

Black and Hispanic patients, non-English primary language speakers, and those living in areas of greater social vulnerability are at increased risk of emergent GB surgery when compared with White, English primary language speakers, and those from well-resourced communities. [11-14] Barriers to timely consultation and surgery among historically marginalized communities include patient- and system-level factors. For example, work conflicts, limited paid time off, long clinic wait times, and limited ability to contact the surgical clinic often preclude the ability of patients with social vulnerabilities to seek a consultation or receive elective, operative care.[15-18]

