Aim 1: Examine racial disparities in outcomes of PCSL patients with symptomatic GB disease with attention to conditional effects of social vulnerabilities. Hypothesis 1.1: Black patients are less likely to undergo cholecystectomy in the elective setting than White patients. Hypothesis 1.2: Time to consultation will modify the effect of race on elective cholecystectomy. Using PennMedicine data we will perform a retrospective cohort study of PCSL patients diagnosed with symptomatic GB disease between Jan. 1 2020 and Sept. 30, 2022. The primary independent variable will be race. Primary outcome will be cholecystectomy. Secondary outcomes will include time from referral to consultation and treatment, completion of consultation, urgency of operative treatment, and cost. Regression models with interaction terms will be used to evaluate effect modification of additional social vulnerability factors (e.g., ethnicity, primary language, insurance, income) on outcomes.

Aim 2: Comparative effectiveness study of telemedicine consultation for symptomatic GB disease in patients with social vulnerability (SV). Hypothesis 2.1: Recruitment will be feasible in the three-month pilot period. Hypothesis 2.2: Time to telemedicine consultation will be shorter than in-person consultation. We will perform a pilot study of telemedicine vs in-person surgical consultation for patients with SV with symptomatic GB disease seen in PCSL clinics between January and June 2023. Rates of surgical consultation will be compared between groups by consultation type. Secondary outcomes will be examined.

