Setting and Participants Patients ages 18+ years with symptomatic cholelithiasis or biliary colic who are a member of a racial or ethnic minority, not primary English speaking, from a low-income neighborhood or underinsured will be identified from the PCSL (see above) and Emergency Department (ED) discharges including referral to surgery. See **Figure** for exclusion criteria. After Institutional Review Board (IRB) approval, potential participants with a new ICD-10 code for symptomatic cholelithiasis or biliary colic seen by a PCSL provider between April 1, and June 30, 2023 will be identified. The diagnosis and discussion with the PCSL provider will be confirmed by chart review to ensure the patient is aware of their diagnosis. Then, patients will be recruited via the electronic health record. Nonresponses will be contacted by phone. If enrollment is lower than required, patients will be approached about participation at the time of the in-person PCSL or ED visit. Participation will be voluntary and informed consent will be obtained. For this pilot study, enrollment will proceed to a maximum of 25 per group. We anticipate between 2-37 eligible patients per week. Participants will receive an incentive of \$20 for participation. Demographics and clinical information will be collected in REDCap, a HIPPA-compliant, secure web application for building and managing online surveys and databases.

Exposure, Intervention Assignment, Covariates and Outcomes

Exposure: Assignment to telemedicine surgical consultation (vs. usual care) during the week of diagnosis of symptomatic cholelithiasis or biliary colic.

Intervention Assignment: Pragmatic randomization will be performed by group enrollment in alternating weeks.

Covariates: Participants will be followed for 6-months from enrollment. Data on patient attributes will include age, race, sex, insurance status, primary language and 9-digit zip code as a proxy for neighborhood income level. Clinical factors will be abstracted from the electronic medical record including comorbid conditions as defined in the Elixhauser Indices [28], bilirubin, liver function studies, ultrasound scan and CT scan results.

Outcomes: Primary outcome will be proportion of patients who undergo surgical consultation. Surgical consultation will be determined via chart review including care everywhere to

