ensure capture of visits outside of Penn Medicine. Secondary outcomes will include time to consultation, proportion to undergo cholecystectomy, time to surgery, and emergent/urgent vs elective operation.

Data Analysis Descriptive statistics will be performed. Univariate comparisons to test hypotheses will be performed using the chi-square test or Fisher's exact test for categorical data and t-test or Wilcoxon rank-sum for continuous data. Statistical analysis will be performed using STATA Version 17 (Stata Corporation, College Station, TX). Stratified analyses will be performed by race, ethnicity, primary language, median neighborhood income, and insurance status as permitted by sample size.

PRELIMINARY STUDY RESULTS and POWER CALCULATIONS

In addition to providing preliminary evidence of the efficacy potential of telemedicine surgical consultations, the goal of the pilot study is to estimate recruitment and retention rates and population variance of social vulnerability factors. Because we want to be powered to detect small effect sizes, ($0.1 \leq d < 0.3$) where d is the standardized difference, we will target enrollment of 20 participants per group to achieve a power of 80%, $\alpha=0.05$. [32]

Limitations

- The study focuses on patients already connected to primary care providers. Many patients with SV may not reach that point in the health system. However, in clinical practice at Penn Medicine it is not uncommon for patients to have insurance that allows primary care at our community sites without providing benefits for surgical care for nonemergency conditions. This approach to patient care exposes patients treated in our community to the excessive clinical and financial risks associated with emergency surgery. Because we will conduct an explanatory analysis of factors associated with surgical consultation and treatment, we will identify barriers to surgical health equity (e.g., insurance coverage) within our system. This will allow us to develop strategies to achieve health equity at the system level.

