- In Aim 1, we will not be able to assess patient preference as a reason for undertreatment. We will be able to identify major structural barriers to care (e.g., primary language, insurance etc.). In the pilot study, we will include items on patient preferences (e.g., refusal to see a surgeon or have an operation). This will allow us to gauge the magnitude of this problem in patients with symptomatic GB disease at Penn Medicine. If this is a big problem, we will have to perform additional qualitative studies to determine optimal solutions.
- Telehealth consultation may not be available to the most vulnerable patients. While that was true historically, during the pandemic studies confirmed that telehealth was used widely, especially among those with social vulnerabilities. Moreover, prior to the pandemic, surgical telehealth was used effectively in our system. In the original study, 79% of patients were able to receive telemedicine surgical visits and only 3% were unable due to language or communication barriers.

Future Directions

This study will provide data to develop targeted solutions to achieve surgical health equity at Penn Medicine. For example, in Aim 1, if we discover that underinsurance is the large barrier to treatment, then expanded professional navigation may be the way forward. If mistrust of the system and fears of surgery emerge as barriers to treatment, then peer navigation may be important. Alternatively, if we find that time off work and transportation to visits preclude surgical treatment, then telemedicine consultations (and resultant elective same day surgery rather than emergency in-patient care), may lead us to the path to health equity. We will test this directly in Aim 2. Improving access to care will result in improved patient and provider satisfaction. We will use this information to convene stakeholders within the system to build a Penn Pathway for symptomatic cholelithiasis and biliary colic. Further, this information will provide direction for the design of a larger trial to test multiple additional approaches to overcome barriers to surgical health equity within Penn Medicine that can be scaled across practices and even beyond the confines of our own network. These data will set the stage for high value care bundles to treat patients with social vulnerabilities within Penn Medicine.

REFERENCES

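### Aim 2 gives no rule for participants without a consultation or operation in the time comparisons (H2.2 and time to surgery), so the named tests would by default compare only those who had the event

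*Combined protocol and SAP*

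**What the plan says.** The Aim 2 statement gives two hypotheses. One concerns time: "Hypothesis 2.2: Time to telemedicine consultation will be shorter than in-person consultation". Under Outcomes, "Primary outcome will be proportion of patients who undergo surgical consultation", and then "Secondary outcomes will include time to consultation, proportion to undergo cholecystectomy, time to surgery, and emergent/urgent vs elective operation". The length of follow-up appears under Covariates: "Participants will be followed for 6-months from enrollment".

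The Data Analysis paragraph names chi-square or Fisher's exact test for categorical data and "t-test or Wilcoxon rank-sum for continuous data", with descriptive statistics and stratified analyses. The readable text does not mention censoring, survival curves, a log-rank or Cox comparison, a value or rank for participants without the event, or an analysis set for the time outcomes. Aim 2 does not define the time origin. Follow-up starts at enrollment, whereas Aim 1 counts from referral.

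The protocol expects participants without the event. Aims and Significance says that barriers "often preclude the ability of patients with social vulnerabilities to seek a consultation or receive elective, operative care". Limitations says that the pilot will record patient preferences such as "refusal to see a surgeon or have an operation".

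**The concern.** A participant who is never consulted within 6 months has no time to consultation. A t-test or rank-sum test leaves out missing values unless one is assigned, so the plan as written leads to a comparison among the consulted. That subset is formed after assignment, and by the primary outcome itself. Time to surgery has the same problem, because it exists only for those who had a cholecystectomy.

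Two things can go wrong. If telemedicine brings in patients who would otherwise not have been seen, and they are seen later than the rest, telemedicine can look slower although its patients overall are seen sooner. If telemedicine speeds up everyone, part of the effect shows as extra consultations and disappears from the time comparison, which then loses power.

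This matters beyond a minor secondary outcome. H2.2 is one of two Aim 2 hypotheses, Equity Plan and Impact names timeliness as a measure of health equity, and Future Directions says the results will guide a larger trial.

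**Working it through.** The documents give no figure on this point to reproduce, so the check is a simulation.

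**Inputs.** From the plan: 20 per group (the enrollment target), alpha 0.05 (taken as two-sided) and 6 months of follow-up (taken as 180 days). Assumed, because the documents give no values: uptake of consultation, distribution of times and size of effect. There were 4,000 replicates per cell (standard error at most 0.8 percentage points).

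**1. Telemedicine speeds up everyone.** Times are exponential. For in-person uptake p by day 180, the hazard is λ = −ln(1 − p)/180, and telemedicine uptake is 1 − (1 − p)^HR. For p = 0.50 and HR 2.5 this is 1 − 0.5^2.5 = 0.823. Percentage of trials that reject, HR 2.5:

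| In-person uptake | Rank-sum, consulted only | Rank-sum, all, tied worst rank | Log-rank, all | Fisher on proportion alone |
|---|---|---|---|---|
| 50% | 9.5 | 59.1 | 64.5 | 47.4 |
| 70% | 23.6 | 64.8 | 74.3 | 43.9 |
| 85% | 41.3 | 66.3 | 78.4 | 15.8 |
| 90% | 49.4 | 67.0 | 79.8 | 3.8 |
| 95% | 59.3 | 67.0 | 78.1 | 0.3 |
| 99% | 66.3 | 67.7 | 78.7 | 0.0 |

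At low uptake, part of the gain re-tests the primary outcome, as the last column shows. At 99% uptake the log-rank lead is test efficiency under proportional hazards and has nothing to do with missing times.

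Smaller effects, consulted only against worst rank:
- HR 2.0: 6.7% vs 37.1% at 50% uptake, 23.4% vs 44.2% at 85%, 37.1% vs 45.9% at 95%.
- HR 1.5: 5% vs 14% at 50%, 9% vs 17% at 85%.
- HR 1.3: 5% vs 9% at 50%, 9% vs 10% at 95%.

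With no effect, consulted-only rejects in 4.6–5.0%, worst-rank in 4.9–5.5% and log-rank in 5.2–6.5%.

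**2. Telemedicine only adds late-seen patients.** A share b of patients face barriers; the rest are readily seen with mean 30 days in both arms. The proportion not yet seen is S(t) = (1 − b)·exp(−t/30) + b·exp(−λ₂t). In person, 10% of barrier patients are seen by day 180, so λ₂ = −ln(0.9)/180 = 0.000585. By telemedicine their mean is 120 days, so λ₂ = 1/120. Uptake is U = 1 − S(180). The consulted-only median solves 1 − S(t) = U/2, and the all-patient median solves S(t) = 0.5.

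For b = 0.5:
- In person: U = 0.5 × 0.9975 + 0.5 × 0.10 = 0.549. At t = 23.0, 1 − S = 0.5 × 0.5355 + 0.5 × 0.0134 = 0.2745 = U/2.
- Telemedicine: U = 0.5 × 0.9975 + 0.5 × 0.7769 = 0.887. At t = 31.8, 1 − S = 0.5 × 0.6535 + 0.5 × 0.2328 = 0.443 = U/2.
- All patients: S reaches 0.5 at 89 days in person and 38.7 days by telemedicine.

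| In-person uptake | Median among consulted, in person vs telemedicine (days) | Median in all patients (days) | Trials with telemedicine significantly slower, consulted only |
|---|---|---|---|
| 55% | 23 vs 32 | 89 vs 39 | 8% |
| 73% | 22 vs 26 | 37 vs 29 | 6% |
| 82% | 21 vs 24 | 29 vs 26 | 5% |
| 91% | 21 vs 22 | 24 vs 23 | 3% |
| 95% | 21 vs 21 | 22 vs 22 | 3% |

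The consulted-only sample medians point the wrong way in 71% of trials at 55% uptake and in 53% at 95%.

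**3. Telemedicine does both.** If it also halves these waits (means 15 and 60 days), the consulted-only medians point the right way. Power to show telemedicine faster is then about 5% among the consulted against 74% with a worst rank at 55% uptake, narrowing to 37% against 45% at 95%.

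**4. Separate check at 25 per group** (the enrollment cap; 182 days; 2,000 replicates). With uptake 50% vs 75% and constant hazards, consulted-only rejects in 8%, worst-rank in 44% and log-rank in 47%. If telemedicine instead adds a quarter of patients, seen at days 60–150, consulted-only medians are about 34 days in person and 48 by telemedicine, and they point against telemedicine in 88% of trials.

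**5. Time to surgery.** If 10% are operated on within 6 months in person (assumed, HR 2.5), power is 1% among those operated on and 20% with a worst rank.

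**The case against.** The plan never says that participants without the event are dropped. The rank-sum test it names works once they are given a tied worst rank. On this view the gap is one missing sentence, not a wrong method. That is fair: the exclusion is an inference from how these tests treat missing values. But nothing in the plan prevents it, and choosing the handling after outcomes are seen could decide the sign of H2.2.

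Read literally, H2.2 may compare only the waits of consultations that take place. Shown beside the proportion consulted, such times are coherent. They are not a comparison of the assigned groups, however, and the Aim 2 exposure is defined as assignment.

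The objections on size carry most weight. No document supports a hazard ratio of 2.5, and the plan itself speaks of small effects. At 1.3, no method has useful power with 20 per group. The risk of a significant wrong-direction result is close to chance above 90% uptake, and in that scenario the worst-rank test is little better there. Participants have consented and know their diagnosis, so uptake may be high. The statement in Limitations that "79% of patients were able to receive telemedicine surgical visits" is not a consultation rate and does not settle the matter. The simulations also treat patients as independent, although assignment alternates by week; correlation within weeks would change every power figure.

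These points limit the harm. They do not supply the missing rule.

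**Conclusion.** The concern holds. The omission is certain from the text; its consequence is conditional. With near-complete consultation it hardly matters. With in-person uptake between about 50% and 85%, and a large effect, the default comparison loses much of the power available from the same patients. At the lower end of uptake it can also show telemedicine as slower when patients overall are seen sooner. All rates, times and hazard ratios behind these figures are assumptions. Time to surgery is probably the more exposed outcome if few are operated on within 6 months, but only one assumed rate was examined.

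The affected outcomes are secondary, in a pilot that also reports the proportion consulted. The plan should be changed, but the primary comparison does not depend on it.

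**What to change.** Add to Aim 2, Data Analysis:
- Time to first surgical consultation and time to surgery are analysed in all participants by assigned arm, from one stated origin. Enrollment is the natural choice, since follow-up runs from it.
- Participants without the event are censored at 6 months or last contact. Kaplan-Meier or cumulative incidence curves are shown, with a log-rank or Cox comparison.
- If the rank-sum test is kept and follow-up is complete, everyone is included and participants without the event share a tied worst rank.
- The analysis states how an operation before any consultation is counted, for example as a competing event.
- Times among those consulted or operated on are descriptive only.

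The cost is wording: same data, same software, no extra patients. The downside is that the result combines whether and how fast patients are seen, so it overlaps with the primary outcome and should be presented that way. The log-rank test also rejected slightly above 5% under no effect at this sample size (5.2–6.5%).

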Scalability Preliminary data from Penn Chart shows that more than 9,400 PCSL patients seen within the last 6 months have a diagnosis of untreated symptomatic gallbladder disease, and less than 1000 have undergone appropriate treatment (see Figure). This proposal will use a robust approach to explain why patients in our community with symptomatic GB disease do not receive timely treatment (Aim1). Then, we will test the ability of telemedicine to improve timely access to surgical care (Aim2). Currently, PCSL and Emergency Medicine providers refer patients to in-person clinic visits with surgeons. These visits typically require at least a half day off from work, if not more. Since the onset of the pandemic, Penn Medicine surgical clinics have integrated telemedicine into routine practice. Telemedicine decreases time off from work and eliminates the need for transportation (two established barriers to surgical care) while promoting surgical health education, the establishment of trust, and ease of communication with the clinic. Patients will be randomized to a telemedicine preoperative surgical consultation or a traditional in-person surgical consultation. The Penn Medicine system has capacity for this volume of surgical referrals across the three downtown hospitals. Patients will be referred to the location that is most convenient for them. This proposal will pilot the use of telemedicine for patients with symptomatic gallbladder disease treated within the community practices of PennMedicine. We propose that, at scale, this initiative will encourage the **development of a Penn Pathway** for symptomatic cholelithiasis and biliary colic to improve patient and provider satisfaction and will show evidence of PennMedicine’s ability to eliminate unnecessary waste in the pathway to surgical health when negotiating **value-based purchasing agreements** with payers.

Equity Plan and Impact

GB disease, associated with obesity, is very common, especially among patients with social vulnerabilities [26, 27]. Guidelines recommend laparoscopic cholecystectomy, a safe and effective same day surgery, for patients with symptomatic cholelithiasis and biliary colic (SGBD). From the literature, we know that delays in care often result in emergent presentation which is significantly associated with increased rates of complications, prolonged hospitalization, and death.[8-10]

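### The pilot is to gauge how common refusal of a surgeon is among symptomatic gallbladder patients, but it enrols consenting volunteers and plans no data from decliners, so it probably understates refusal of consultation.

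*Combined protocol and SAP*

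**What the plan says.** Four statements in the Limitations section of the combined protocol and SAP form a chain.

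- Aim 1 cannot supply the information: "In Aim 1, we will not be able to assess patient preference as a reason for undertreatment".
- The pilot will: "In the pilot study, we will include items on patient preferences (e.g., refusal to see a surgeon or have an operation").
- The result is extended beyond the pilot: "This will allow us to gauge the magnitude of this problem in patients with symptomatic GB disease at Penn Medicine".
- A decision follows from it: "If this is a big problem, we will have to perform additional qualitative studies to determine optimal solutions".

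The Aim 2 section on setting and participants says who will be in the pilot. They are adults with symptomatic cholelithiasis or biliary colic who meet at least one social-vulnerability criterion. They are contacted through the electronic health record, and then: "Nonresponses will be contacted by phone". If enrolment falls short, they are approached in person. Of those contacted: "Participation will be voluntary and informed consent will be obtained".

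What participants join is described in two ways. The Scalability section says: "Patients will be randomized to a telemedicine preoperative surgical consultation or a traditional in-person surgical consultation". The Aim 2 exposure definition says: "Assignment to telemedicine surgical consultation (vs. usual care) during the week of diagnosis of symptomatic cholelithiasis or biliary colic".

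The Aim 2 power section lists estimation of recruitment and retention rates among the pilot's goals. It does not mention reasons for declining.

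**The concern.** The quantity to be measured, unwillingness to see a surgeon, is itself a plausible reason not to join a study of surgical consultation. Selection would then act directly on the estimate, and enrolling more volunteers would not correct it.

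The plan names the pilot as its source on refusal and intends to act on the result. Future Directions chooses among responses (professional navigation, peer navigation, telemedicine) according to which barrier emerges. An understated refusal figure would make preference look less important than it is when that choice is made.

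**Working it through.** **No figure to reproduce.** The documents state no refusal rate, no consent rate and no target precision for the preference items. The check therefore has two parts: a comparison of populations, and an illustration with assumed inputs.

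**Populations compared.**

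- Target of the inference (Limitations): patients with symptomatic gallbladder disease at Penn Medicine.
- Source of the data (Aim 2): consenting volunteers with social vulnerability, with a target of 20 per group (40 in total) and a maximum of 25 per group (50 in total).
- Link between the two: none described. The plan mentions no survey of decliners, no recorded reasons for declining, and no comparison of enrolled with eligible non-enrolled patients.

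The social-vulnerability restriction is probably the smaller part of the gap. The Equity section's preliminary data put 91% of PCSL patients with the condition in low-income neighbourhoods. That criterion alone would leave out at most about 100% − 91% = 9% of them. Consent is the larger issue.

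**Direction and possible size.** Let *p* be the true proportion of eligible patients who would refuse to see a surgeon. Let *k* be the consent probability of refusers divided by that of the others. The proportion of refusers among enrolled patients is then

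observed = *pk* / (*pk* + 1 − *p*).

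This equals *p* when *k* = 1 and is below *p* whenever *k* < 1. Sample size does not enter. With *p* = 0.30 (assumed):

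- *k* = 1/2: 0.15 / (0.15 + 0.70) = 17.6%
- *k* = 1/6: 0.05 / (0.05 + 0.70) = 6.7%

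Across a range of assumed values:

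| True refusal | *k* = 1 | *k* = 0.5 | *k* = 0.25 | *k* = 0.1 | *k* = 0 |
|---|---|---|---|---|---|
| 10% | 10% | 5.3% | 2.7% | 1.1% | 0% |
| 30% | 30% | 17.6% | 9.7% | 4.1% | 0% |
| 50% | 50% | 33.3% | 20.0% | 9.1% | 0% |

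**Sampling error is a separate matter.** At 6.7%, the expected count is 0.067 × 40 = 2.7 to 0.067 × 50 = 3.3, or about 3 patients. The exact 95% limits for 3 of 40 are 1.6% to 20.4%, and for 3 of 50 they are 1.3% to 16.5%. Both intervals exclude the assumed true value of 30%, because they describe consenters only.

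**The case against.** The strongest objection is that the plan does not say who receives the preference items. It says only that they are part of the pilot. Estimating a recruitment rate requires a count of patients approached, so items asked at the recruitment contact would be compatible with the text. This stands as a limit: that the items go to consented participants is an inference from their placement in the pilot, the consent requirement and the absence of any described data from decliners.

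A reader might go further and infer that refusers are screened out altogether, or that the primary outcome describes only patients already willing to be seen. The documents do not support either reading. The Aim 2 exposure definition calls the comparator usual care, so joining need not mean agreeing to attend. The primary outcome is the proportion who undergo consultation, which presupposes that some participants will not. Participants are followed for six months, so non-attendance and refusal of an operation can both be seen. Refusers are likely to be under-represented, not absent.

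A reader might also infer that the follow-up qualitative work will not be triggered, or that undertreatment will be put down to structural barriers by default. Neither can be shown. The plan sets no threshold for calling refusal a large problem, and Future Directions names mistrust and fear of surgery as possible barriers with their own response.

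Finally, volunteer selection affects any consented pilot, and the claim at issue is a sentence in Limitations, not an aim or endpoint. That is fair. It limits the importance of the point but does not remove the mismatch, because selection here acts on the very quantity the sentence promises to gauge.

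**Conclusion.** The point holds as a mismatch between the sample and the stated inference. A consented, socially vulnerable sample with no described data from decliners cannot gauge refusal of consultation among all patients with the condition at Penn Medicine.

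The expected error is downward. That rests on one assumption, that patients unwilling to see a surgeon consent less often than others; if they consent equally often, this bias disappears. Its size cannot be computed from the documents, and every percentage in the illustration is conditional on assumed inputs.

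The comparison between the two consultation groups is not called into question by this point. It should still be dealt with before recruitment starts, because reasons for declining are hard to recover afterwards.

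**What to change.** At the EHR, phone or in-person recruitment contact already planned, log one disposition for every eligible patient: enrolled; declines to see a surgeon; declines an operation; declines research only; declines without a reason; or not reached.

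Report two things, and keep their denominators apart:

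1. Refusal among patients reached.
2. Bounds over all eligible patients. With *N* eligible, *R* known to refuse and *U* either not reached or declining without a reason, the bounds are *R*/*N* (none of the unknowns refuse) and (*R* + *U*)/*N* (all of them refuse).

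Use these figures for the decision on further qualitative work. Limit the Limitations statement to eligible patients with social vulnerability. If decliner data are not collected, limit it to enrolled participants.

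The cost is one optional question, one screening-log field and matching IRB wording. The drawback is that some decliners will give no reason and some patients will not be reached. The bounds are *U*/*N* wide, so if 40% of eligible patients were in the unknown group (an assumed figure), they would span 40 percentage points. Bounds that wide would at least show how little the pilot can say about refusal.
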